Study Design:	
• Multi-center clinical trial at up to 30 investigational sites• Prospective, randomized, concurrently-controlled trial• Control: Instrumented posterolateral fusion• 200 Minimum/500 Maximum Investigational and 100 Minimum/250 Maximum Control patients using 2:1 randomization• Up to 60 non-randomized investigational training cases (two per site)
Study Duration/ Follow-up Period:	Study Duration: 48-58 months Follow-up: 6 week, 3, 6, 12 and 24 month postoperative time points, and annually thereafter as required by FDA
Indication for Use:	The AFRS Study will include patients who have lateral, lateral recess and/or central stenosis at the L3 to S1 level requiring decompression and facetectomy. The operative level will receive either the test or control treatment. Adjacent lumbar vertebrae levels may be treated through decompression as required to treat stenosis that does not result in complete facetectomy or fusion.
Inclusion Criteria	
• Is 21-85 years of age and skeletally mature;• Undergone at least six cumulative months of conservative treatment prior to surgery including any of the following: medications, NSAIDs, physical therapy, bracing, chiropractic manipulation, modified activities of daily living, epidural injections, facet block injections;• Lateral, lateral recess and/or central canal stenosis as demonstrated by compression of the thecal sac and/or cauda equina, nerve root impingement by either osseous or non-osseous elements or evidence of hypertrophic facets with encroachment into the central canal or lateral recess at the involved level as determined by MRI, CT scan, plain film or myelography;• Disc height measuring ≥ 4 mm at the operative level;• Persistent leg, thigh and/or buttock symptoms, including pain, numbness, burning or tingling with a minimum leg pain score of 40mm as measured with the Visual Analogue Scale (VAS) Index;• A score greater than 2 on a scale of 1-5 on the Zurich Claudication Questionnaire (ZCQ) Symptom Severity (SS) Score;• A score greater than or equal to 2 on a scale of 1-4 on the ZCQ Physical Function (PF) Score;• A candidate for a decompression with full facetectomy at the operative level;• A candidate for an instrumented posterolateral fusion;• Willing and able to comply with postoperative and routinely scheduled clinical and radiographic evaluations;• Lives in the immediate area and has no plans to relocate to another geographic

Exclusion Criteria

area before the completion of the study, or lives outside the immediate area and is willing to comply with scheduled postoperative visits with a designated physician;

- Signed a patient informed consent specific to this study.
- Previous surgical procedure at the operative or adjacent level except for one of the following: micro-discectomy, laminectomy, lamino/foraminotomy, rhizotomy, IDET, and/or interspinous spacer;
- Previous lumbar fusion or disc replacement procedure;
- Osteoporosis as defined by Simple Calculated Osteoporosis Risk Estimation (SCORE) screening questionnaire score of 6 or greater and DEXA bone density measured T-score ≤ -2.0 ;
- Greater than Grade I spondylolisthesis or retrolithesis, as defined by the Meyerding Grading Classification, at the operative level;
- Spondylolisthesis any grade, as defined by the Meyerding Grading Classification at levels other than at the operative level;
- Scoliosis of the lumbar spine (defined as more than 11° Cobb angle), as indicated by plain X-ray films;
- Primary diagnosis of discogenic back pain due to torn, herniated, inflamed or irritated disc or other pathology where the patient exhibits axial back pain from degenerative disc disease;
- Acute traumatic pars fracture at the operative or adjacent level vertebral body;
- Spinal stenosis at more than three lumbar segments;
- Experienced acute trauma to the lumbar spine within the last 24 months;
- Active infection at the operative level, or a systemic infection including prior or pending treatment for HIV or Hepatitis C;
- Physically or mentally compromised (*i.e.*, being currently treated for a psychiatric disorder, senile dementia, Alzheimer's disease, presence of alcohol or substance abuse) in a manner that would compromise his or her ability to participate in the clinical study;
- Diagnosed systemic disease (*i.e.*, Paget's disease, muscular sclerosis, amyotrophic lateral sclerosis (ALS), renal osteodystrophy, metastasis to vertebrae, Lupus, or ankylosing spondylosis) that may affect the patient's welfare or overall outcome of the research study;
- Immunologically suppressed or immunocompromised;
- Insulin-dependent diabetes mellitus (type I diabetes);
- Currently undergoing long-term steroid therapy (treated in the last 6 months with systemic corticosteroids);
- Metabolic bone disease (*i.e.*, osteomalacia, and/or osteogenesis imperfecta);
- Is of child-bearing potential, and is either pregnant or interested in becoming pregnant during the duration of the study;
- Medically significant obesity as defined by a Body Mass Index (BMI) of > 40 kg/m². BMI = (weight in pounds \times 703) \div (height in inches \times height in inches);
- Active malignancy: a history of any invasive malignancy (except non-melanoma skin cancer), unless the patient has been treated with curative intent and there have been no clinical signs or symptoms of the malignancy for at least 5 years;

- Known allergy to cobalt chromium or titanium;
- Used any investigational drug or device within the past 30 days;
- Pending litigation related to back pain or injury;
- Is a prisoner.

Primary Endpoint: The primary study endpoint for this study is individual patient success at 24 months. Individual patient success will be defined as follows:

- Improvement in the ZCQ by a minimum of 0.5 for both Symptom Severity (SS) and Physical Function (PF) scores at 24 months as compared to baseline.
- Maintenance or improvement in neurological outcome at 24 months.
- No subsequent surgical intervention at the level of treatment (including device failures requiring revision, removal, re-operation and supplemental fixation).
- No serious device-related adverse events.

Secondary Endpoints:

- Maintenance or improvement of the components of the primary ZCQ;
- Maintenance or improvement in patient function, as measured by the Oswestry Disability Index (ODI) questionnaire;
- Maintenance or improvement of the leg and back VAS pain scores;
- Maintenance or improvement in the components of the SF-36 Quality of Life Questionnaire;
- Changes in quantitative radiographic measures including disc height, vertebral range of motion and translation;
- Changes in qualitative radiographic measures including fusion; assessment, device migration and presence of radiolucencies;
- Radiographic Success
- Maintenance or improvement in neurological status;
- Incidence, severity and device or procedure relatedness of all adverse events over the 24-month study assessment period;
- Components of primary endpoint (surgical revisions, reoperations, removals, supplemental fixation);
- Return to normal activities of daily life;
- Change in work status and time to return to work;
- Narcotic medication usage;
- Length of hospital stay;
- Duration of surgical procedure and instrumentation time;
- Blood loss;
- Rehabilitation utilization.

Investigational Sites: Up to 30 Investigational Sites

Study Sponsor: Globus Medical, Inc.
[name]
[name]
[name]
[contact]

LIST OF ABBREVIATIONS AND DEFINITION OF TERMS

ACRONYM	DESCRIPTION
AE	Adverse Event
AFRS	ACADIA [®] Facet Replacement System
AP	Anterior-Posterior
BMI	Body Mass Index
CRF	Case Report Form
CS	Clinically Significant
CT	Computed Tomography
DEXA	Dual Energy X-ray Absorptiometry
GCP	Good Clinical Practice
HIV	Human Immunodeficiency Virus
ICH	International Conference on Harmonization
ICF	Informed Consent Form
IDET	Intradiscal Electrothermic Therapy
IEC	Independent Ethics Committee
IRB	Institutional Review Board
MRI	Magnetic Resonance Imaging
NCS	Not Clinically Significant
NSAIDs	Nonsteroidal Anti-Inflammatory Drugs
ODI	Oswestry Disability Index
PF	Physical Functioning
PHI	Personal Health Information
PI	Principal Investigator
PLF	Posterolateral Lumbar Fusion
QA	Quality Assurance
SAE	Serious Adverse Event
SLR	Straight Leg Raise
SS	Symptom Severity
UADE	Unanticipated Adverse Device Effect
US	United States
VAS	Visual Analog Scale
ZCQ	Zurich Claudication Questionnaire

1.0 INTRODUCTION

1.1 Background

Chronic spinal pain is the leading cause of disability in the industrialized world.¹ It has been estimated that 65% to 80% of the people in the United States will suffer an episode of low back pain during their lifetime.² In 1997, low back pain was estimated to have a total impact of \$171 billion in the industrial setting of the United States. In 1990, the estimated cost of medical treatment for low back pain alone was \$13 billion.³ Low back pain is acknowledged as a large, costly and growing problem in industrialized countries.

The origin of low back and leg pain is varied and may include muscular, neurological and skeletal components. The most common indication for elective lumbar surgery is pain that is refractory to non-surgical treatment. The indications for reconstructive surgery to treat painful spinal conditions include instability, degenerative spondylolisthesis, scoliosis, stenosis and degenerative disc disease.⁴ Many of these conditions are associated with degeneration of the spine which often occurs at an early age and progresses as the patient gets older.⁵ This degeneration is associated with the mobile joint segments that comprise the lumbar spine.

At each level of the spine there is a three joint complex that allows for motion of the segment while preserving stability. This three joint complex consists of the disc and two facet joints. While the disc is a fibrocartilagenous joint, the facet joints are synovial joints consisting of articular cartilage, synovial fluid and fibrous capsule. The nature of the degenerative process differs between the discs and facet joints. However, due to their close relationship and function, changes in one joint will invariably affect the remaining two. It has been shown that changes to the disc structure are accompanied by facet osteoarthritis.⁶ The two lowest motion segments of the lumbar spine are most affected by this degeneration process with disc degeneration and facet osteoarthritis increasing with age.^{7,8,9} The degeneration of the motion segment leads to abnormal motion, instability and joint collapse. Eventually this can lead to spondylolisthesis due to asymmetric alignment of the facets with associated facet osteoarthritis and stenosis that contributes to increased pain and loss of function.

Facet joint osteoarthritis due to wear and motion is characterized by facet hypertrophy, thickening of the joint and osteophyte formation resulting in lateral, lateral recess and/or central canal stenosis. Mooney and Robertson demonstrated that the facet joint contributed to pain through the use of intra-articular facet injections.¹⁰ It is estimated that 15-40% of low back pain is attributed to the facet joint.^{11,12} Treatments for facet generated problems include decompression, facetectomy and posterior fusion. Although these treatments address the symptoms of pain, they may result in further destabilization and in the case of fusion loss of motion. It has also been reported that fusion with loss of motion transfers stresses to the adjacent motion segments creating additional degeneration and instability in these adjacent segments.^{13, 14}

Historically, degeneration and instability of the joint and associated stenosis has been addressed with fusion. There could be a meaningful patient benefit by replacing the current practice of posterior fusion with facet arthroplasty. This approach involves the replacement of the degenerated facet with an articulating joint while resolving the associated stenosis. A facet arthroplasty system allows for an anatomic reconstruction of the facet joint after decompression and removal of the degenerated facet. Like the original facet joint, the replacement implant is designed to reproduce facet motion while restoring normal stability and kinematics. Instrumentation allows for precise and reproducible placement of the inferior and superior articulating implants. The cobalt chrome articulating components are aligned and secured at their natural anatomical position on the pedicle.

The ACADIA[®] Facet Replacement System (AFRS) has been designed on the principals that have allowed other total joint arthroplasty procedures to provide significant patient benefits. These guiding principals include:

- Anatomically-based implant design
- Reproducible surgical technique
- Elimination of pain

Globus Medical acquired the ACADIA[®] Facet Replacement System from Facet Solutions, Inc., in January 2011, and is now the sponsor of the associated Investigational Device Exemption (IDE) clinical trial.

1.2 Device Name

The device under clinical investigation is the ACADIA[®] Facet Replacement System (AFRS).

1.3 Purpose

The purpose of this study is to evaluate the safety and effectiveness of the AFRS in patients with lateral, lateral recess and/or central canal stenosis due to facet degeneration at a single level from L3 to S1 who require a lumbar decompression and facetectomy compared to an instrumented posterolateral fusion control group. Safety of the AFRS device will be evaluated by the incidence, severity and device or procedure relatedness of all adverse events over the 24 month assessment period as compared to the control group. Effectiveness of the AFRS will be based on the improvement in symptom-related questionnaire scores, function, and neurological status.

1.4 Intended Use

The AFRS device is intended for use in patients with acquired degenerative lateral, lateral recess and/or central canal stenosis at a single level from L3 to S1 that require decompression and facetectomy and have failed to improve with at least six cumulative months of conservative treatment.

Acquired Degenerative Stenosis is defined as a narrowing of the lateral, lateral recess and/or central canal resulting in compression of the thecal sac and/or cauda equina, nerve root impingement by either osseous or non-osseous elements or evidence of hypertrophic facets with encroachment into the central canal or lateral recess at the involved level as determined by MRI, CT scan, plain film or myelography.

In addition, patients should be candidates for, and willing to undergo, an instrumented posterolateral fusion control procedure for the treatment of their acquired degenerative stenosis.

1.5 Study Objectives

The primary objective of this study is to evaluate the safety and effectiveness of the AFRS device through 24 postoperative months compared to an instrumented posterolateral fusion procedure.

More specifically, the primary study objective is to demonstrate that patient success, evaluated at 24 months in patients treated with the investigational device, is not inferior to subject success at 24 months in patients treated with the control procedure, where patient success is based on the following defined measures: The Zurich Claudication Questionnaire (ZCQ), neurological deficit, and the need for subsequent surgical intervention (at the level of treatment) and/or device removal and absence of serious, device-related adverse events.

Patients will also be evaluated during the course of the study for all adverse events and surgical interventions, and the relationship of these events and interventions to the investigational device. All adverse events and surgical interventions will be tabulated and reported for each assessment time period.

[Redacted]

[Redacted]

[Redacted]

[Redacted]

[Redacted]

3.0 STUDY DESIGN AND METHODOLOGY

3.1 Study Design

The pivotal evaluation of the AFRS investigational device will incorporate a multi-center, prospective, randomized, and concurrently controlled study design. Up to 30 sites will enroll and treat a minimum of 300 patients and a maximum of 750 patients into the study. In addition, up to 60 training cases (two per clinical site) may be completed by participating investigators, at the discretion of the Sponsor and participating site clinicians.

The investigational group will consist of at least 200 patients who receive the AFRS device. The control group will consist of at least 100 patients who will receive an instrumented posterolateral fusion. This number is based upon the sample size required to provide reasonable assurance of safety and effectiveness using the concurrent control and allowing for 15 percent loss to follow-up. The patients will be allocated to treatment assignment using a 2:1 randomization scheme.

The outcome measures in this study will include the following: the SF-36 questionnaire, the ZCQ, the ODI, a neurological assessment, a symptomatic pain assessment, as measured with the VAS Index, a patient satisfaction questionnaire, and an independent radiological assessment. In addition, outcome measures will be included to support potential reimbursement with healthcare providers. Patients in both treatment groups will be followed for 24 months postoperatively.

3.2 Study Scope

3.2.1 Participating Institutions

The pivotal trial will utilize a maximum of 30 clinical sites. A list of participating institutions will be provided semi-annually to the FDA as required by regulations.

3.2.2 Patient Population

The AFRS Study will include patients as specified in the Inclusion/Exclusion criteria. Study patients will have lateral, lateral recess and/or central stenosis at a single level from L3 to S1 requiring decompression and facetectomy. Detailed enrollment criteria can be found in the Patient Selection section of this Protocol.

Patients will receive either the investigational or control treatment, using a posterior approach through a midline incision to treat lateral, lateral recess and/or central canal stenosis. All patients will receive a decompression and complete facetectomy. The operative level will receive either the test or control treatment. Up to two adjacent additional levels may be treated through decompression as required to treat stenosis that does not result in complete facetectomy or fusion.

Patients randomized into the investigational group will receive the AFRS device. Those randomized to the control group will receive an instrumented posterolateral fusion.

If the assigned device cannot be placed in the patient during the surgical procedure, this patient will be considered a treatment failure. This patient should receive treatment at the discretion of the principal investigator and must be followed per the protocol through hospital discharge and/or the resolution of any procedure-related adverse events that have occurred.

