4.0 PATIENT SELECTION AND ENROLLMENT

All patients presenting with acquired degenerative lateral, lateral recess and/or central canal stenosis at a single level from L3 to S1 who require decompression and facetectomy and have failed to improve with at least six months of conservative treatment are potential study candidates and will be approached for consent prior to any data collection by a member of the institution's research team. A screening and enrollment log will be provided to study sites to maintain a cumulative log of all screened patients.

Every effort will be made to establish eligibility of the participants prior to enrollment. Only patients who meet all eligibility criteria and have signed an IRB/IEC approved consent form are considered to be enrolled in the study. Patients who are consented but not randomized or randomized but are withdrawn prior to initiation of surgical procedures are considered a screen failure for this study. Reasons for screening failure will be documented on the site screening log. All treated patients will be evaluated, as defined by protocol through 24 months, and annually thereafter as required by FDA.

Patients may not be enrolled in the AFRS study without first granting their consent. No study specified procedures may be completed until patient has signed an approved Informed Consent form. The informed consent process is accomplished by providing the patient with a copy of and allowing the patient adequate time to review, the Informed Consent Form. The contents of this form are discussed by the participating clinical trial site staff with the patient, while allowing adequate time for questions. Patients indicate they are willing to participate in the study, by signing and dating the site's current IRB/IEC approved Informed Consent form.

A patient should not sign the Informed Consent Form if s/he is not willing to accept either the investigational or control treatment as established by the randomization process. Following consent, the patient will be randomized into either the AFRS (investigational) or posterolateral fusion (control) group.

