All patients treated in the study are considered to be "follow-up eligible" and will be required to adhere to the follow-up schedule as outlined in **Appendix 1**. Patients that withdraw consent after receiving treatment will not be required to undergo follow-up after withdrawal; however, these patients will still be considered part of the patient cohort. No patient will be removed from the study unless the patient has withdrawn his or her consent before treatment or no treatment was ever attempted.

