5.7 Patient Discontinuation

All patients enrolled into the current study and who have undergone one of the study treatments, will be followed for 24 months postoperative and until all FDA requirements are met, potentially up to 10 years postoperative. Acceptable reasons for not evaluating a patient through the follow-up period include:

- a) Patient Lost to Follow-Up: Unable to locate patient despite documented attempts to notify the patient via telephone and by certified mail. A patient will not be considered lost to follow-up until the last scheduled follow-up visit (24 month study time point).
- b) Patient Request to Terminate: The patient requests to terminate his/her involvement in the study, therefore withdrawing his/her consent to participate in the study (the investigator must thoroughly document the reasons for termination).
- c) Patient Death: If possible, an autopsy and/or death certificate should be obtained in order to document the cause of death.

If a patient discontinues from the study (regardless of the reason), the investigator will record the reason for withdrawal on the appropriate CRFs. Every effort shall be made to have discontinued patients (as appropriate) return for an “Early Termination Visit” to collect the required safety evaluations as detailed in the protocol.

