8.0 STATISTICAL ANALYSIS PLAN

8.1 Analysis Populations

Primary Analysis Population:

The principal analysis of the primary and secondary endpoints will utilize the intent-to-treat (ITT) patient population. The ITT population will include all randomized subjects for whom surgery is attempted. Subjects for whom surgery is attempted but not successfully completed will be considered treatment failures. Randomized subjects in whom surgery is not attempted will be described in detail in a separate section of the study report.

Secondary Analysis Populations:

The primary and secondary objectives will be further analyzed using an as-treated (AT) analysis performed on all randomized subjects according to the treatment actually received.

The primary and secondary objectives will be further analyzed using a per protocol (PP) analysis performed on an evaluable patient population. The evaluable population will consist of all ITT subjects that: [1] meet critical study eligibility criteria and have no significant protocol deviations based on Clinical Events Committee assessment; [2] have the assigned procedure completed; and [3] completed the 24-month follow-up assessment.

Training Population:

This patient population will include all non-randomized AFRS treated patients enrolled during the pivotal phase of the trial as training cases at the site. A maximum of two patients per site for a total of 60 patients will be included in this cohort. Training cases will be described separately from randomized patients in the final study report and will be presented primarily using descriptive statistics. This patient population will be used to understand the learning curve in the use of the device by assessing the results of the Training cases relative to those obtained in the Treatment group arm of the randomized study.

An additional presentation of the safety data in which all of the patients treated with the AFRS device (non-randomized and randomized) are combined as one cohort and compared to the control group will be included.

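### Patients whose assigned device cannot be placed stay in the ITT set, but sections 3.2.2 and 5.3 do not require their 24-month data, so missing secondary and late safety data depend on procedural failure

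*Combined protocol and SAP*

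**What the plan says.** Section 3.2.2 fixes the primary outcome: "If the assigned device cannot be placed in the patient during the surgical procedure, this patient will be considered a treatment failure". It leaves treatment to the investigator and then says the patient "must be followed per the protocol through hospital discharge and/or the resolution of any procedure-related adverse events that have occurred". It asks for no visit beyond that.

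Section 5.3 covers an overlapping situation. If the surgeon decides during the operation on a procedure other than the one intended, the patient is withdrawn and followed for safety in a separate Not Treated cohort. It gives no length for that follow-up.

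Other sections keep these patients in. Section 8.1 states: "The ITT population will include all randomized subjects for whom surgery is attempted". It adds: "Subjects for whom surgery is attempted but not successfully completed will be considered treatment failures". On use of that population: "The principal analysis of the primary and secondary endpoints will utilize the intent-to-treat (ITT) patient population". Section 4.0 says: "No patient will be removed from the study unless the patient has withdrawn his or her consent before treatment or no treatment was ever attempted". Section 5.6 continues safety and effectiveness follow-up after removal, revision, reoperation or supplemental fixation. Section 1.3 compares safety with control over 24 months.

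**The concern.** A patient whose device is taken out shortly after surgery is followed to 24 months under section 5.6. A patient whose device could not be put in may have no visit after discharge under section 3.2.2. Both are treatment failures and both belong to the ITT population. The visible text gives no reason for treating their data differently.

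Failure status supplies the primary outcome without further visits. It supplies no ZCQ, VAS or SF-36 value, and it does not record a late adverse event or a later operation at the index level. Section 8.7 allows labeling claims on the first five secondary objectives, at 24 months only. In listed order these are ZCQ physical function, ZCQ symptom severity, back pain VAS, and the SF-36 physical and mental composites. Section 8.7 also tests the 24-month composite of revision, reoperation, removal and supplemental fixation.

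A site that follows the plan as written can therefore produce missing data, and the cause is failure of the procedure rather than ordinary dropout. The per-protocol set cannot contain these patients, because it requires the assigned procedure to be completed. The ITT and as-treated analyses are the ones that can, and neither is assured of their 24-month values.

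**Working it through.** No figure in the plan is at issue, so the main check is to apply each rule to one patient: randomized to AFRS, surgery begun, device not placed, another procedure performed.

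- **3.2.2:** primary failure; required follow-up stops at discharge or when procedural events have settled.
- **5.3:** withdrawn; safety follow-up in a separate cohort, length not stated.
- **4.0, removal rule:** treatment was attempted, so the patient is not removed.
- **4.0, visit duty:** "All treated patients will be evaluated, as defined by protocol through 24 months, and annually thereafter as required by FDA". This reaches the patient only if an attempted placement counts as treated.
- **5.7:** 24-month follow-up for patients who have undergone one of the study treatments. It arguably reaches a conversion to instrumented fusion, but not a patient who received neither study treatment.
- **8.1:** in the ITT population for primary and secondary endpoints, as a failure.

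Sections 5.3 and 8.1 cannot both be met if withdrawal means leaving the analysed cohort. Sections 3.2.2 and 8.1 can both be met, but the 24-month secondary data that the ITT analysis needs are then not required.

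**Illustration of size.** The visible text gives no non-placement rate and no event rates. All three inputs below are assumptions.

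- Share of the AFRS arm not placed, k/N: 1% to 5%. That is 2 to 10 patients of 200 (the minimum arm) or 5 to 25 of 500 (the maximum arm).
- 24-month event rate in placed patients, e0: 10%.
- 24-month event rate in unplaced patients, e1: 20% to 40%.

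Full-cohort rate = [e0 × (N − k) + e1 × k] / N. If the unplaced are left out, the observed rate is e0. The understatement is therefore (k/N) × (e1 − e0).

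- Low end, N = 200, k = 2, e1 = 20%: (0.10 × 198 + 0.20 × 2) / 200 = 20.2 / 200 = 10.1%, against 10% observed. Understatement 0.1 points.
- High end, N = 200, k = 10, e1 = 40%: (0.10 × 190 + 0.40 × 10) / 200 = 23 / 200 = 11.5%, against 10% observed. Understatement 1.5 points.

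The rate in placed patients has to be subtracted. Multiplying the share by e1 alone would give 0.2 to 2.0 points and overstate the effect. The result depends only on the share, so it is the same at N = 500. Widening e1 to 30-100% gives 0.2 points (1% × 20 points) to 4.5 points (5% × 90 points). If e1 equals e0 the effect is zero, and if e1 is below e0 the sign reverses.

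**The case against.** The strongest reply is that much of the apparent contradiction dissolves on close reading. The list in section 5.7 headed "Acceptable reasons for not evaluating a patient through the follow-up period include" applies to patients who have undergone a study treatment, so it does not by itself contradict section 3.2.2. The removal rule in section 4.0 concerns cohort membership. The same section lets a patient who withdraws consent after treatment stop visits and still belong to the cohort, and its visit duty attaches to treated patients. Section 8.1 says who is analysed, not how long visits continue. Section 3.2.2 sets a minimum and does not forbid later visits. Section 5.3 provides some safety follow-up, and procedural events are covered through discharge or resolution. The numbers are small beside the 15 percent loss to follow-up allowed for in section 3.1.

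These points narrow the finding. The weight rests on section 8.1 set against sections 3.2.2 and 5.3, with the section 4.0 removal rule and section 5.6 in support. What stands is that no rule clearly requires 24-month data from every patient whom section 8.1 puts in the ITT population.

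A reader might infer more than that, and the documents do not support it:

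- **That the worst outcomes are being dropped, in favour of the arm with more failed placements.** The documents neither rank these patients nor count them. An AFRS patient who ends up with a fusion has received the control treatment, and including that outcome in the AFRS arm would dilute a difference, which in a non-inferiority comparison could help AFRS.
- **That 24-month data will not exist.** They are not required, but sites may collect them, and section 5.7 arguably reaches conversions to fusion.
- **That the labeling-claim endpoints will be predicted from patients with successful implants.** The analysis methods for those endpoints are redacted. The visible text attaches prediction only to the surgical composite, which is not among the five.

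**Conclusion.** The concern holds in a limited form. Sections 3.2.2 and 5.3 leave 24-month secondary scores and later safety and reoperation data uncollected or undefined for patients whom section 8.1 places in the ITT population. Missingness then depends on procedural failure. The primary endpoint is not affected, because sections 3.2.2 and 8.1 both count these patients as failures.

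Direction and size are unknown. The 0.1-1.5 point figure is an illustration under three assumed rates, none taken from the documents. If non-placement is rare, the effect is likely to be small. How missing secondary values would be handled cannot be checked in the visible text. The change is still worth making, because visits that were not made cannot be recovered later.

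**What to change.** Reconcile sections 3.2.2, 5.3, 5.7 and 8.1 together. An edit to section 3.2.2 alone would leave section 5.3 withdrawing patients whom section 8.1 analyses. The reconciled text should say that every randomized patient with attempted surgery:

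- stays in the study, with data collected through 24 months on the Appendix 1 schedule unless the patient withdraws consent, dies or is lost to follow-up;
- is analysed in the assigned arm for the ITT secondary and safety analyses;
- keeps primary-endpoint failure status where sections 3.2.2 and 8.1 assign it.

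This concerns data collection and analysis only. Treatment of these patients stays as the protocol states.

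The cost is protocol wording and standard visits for a small number of patients who have already consented. AFRS safety and secondary results may look slightly less favourable.
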